4.4.2.2 Telemetry

Ambulatory cardiac monitoring (ACM) will be performed using the SL2400 portable monitor (Spacelabs Healthcare, USA) from -1 hour (pre dose) to 24-hour post dose at Visits 2, 3 and 4, and from -1 hour to 24 hours post dose on Day 19 (Visit 4). The Investigator or his/her delegate will review the recordings. A print out will be signed and dated by the Investigator and filed with the CRF.

4.4.3 Vital signs

4.4.3.1 Blood pressure and heart rate

Sitting blood pressure and pulse rate will be measured at the timepoints (shown in Table 2) at Visits 2 and 3 (single doses) and after the first and last multiple doses (ie on Days 13 and 19 [Visit 4]). Vital signs will also be taken at Visit 1b (Screening) and Visit 5 (Follow-up).

On each study day, sitting blood pressure and pulse will be measured using a semi-automatic blood pressure recording device with an appropriate cuff size, after volunteers have been sitting for at least 10 minutes. These data will be entered into the CRF.

4.4.4 Other safety measurements (Not applicable)

Not applicable.

4.5 Genetic measurements and co-variables

4.5.1 Collection of samples for genetic research

Volunteers will provide a blood sample as per the inclusion criteria and visit schedule.

A single venous blood sample will be collected into a 10 mL polypropylene tube containing ethylenediamine tetra-acetic acid (EDTA) and gently inverted a minimum of five times to mix thoroughly. Tubes will be labelled with labels which details study code, volunteer ID (enrolment number and/or randomisation number), sample type, protocol timepoint, and visit number and unique barcode. No personal identifiers (volunteer name, initials or date of birth) will be placed on the tube or accompanying documentation. A record of the date of the volunteer consent to the genetic research and the date of the blood sample collection will be recorded in the appropriate section of the CRF.

Genotype is a stable parameter, therefore if for any reason the blood sample is not drawn at Visit 2 it may be taken at any visit until the last study visit. The genetic blood sample should ideally be drawn through the same cannula used to draw blood samples required for the main study.

4.5.1.1 Sample processing and shipping

Samples will be frozen (-18°C or below) and transported to the relevant DNA extraction laboratory within one month of collection and must remain frozen at all times.

Where possible samples should be shipped in batches and shipment should be coordinated with the receiving site to ensure that samples arrive within working hours. A requisition sheet, detailing the protocol study number, centre number, enrolment number and/or randomisation code and date of sample collection, should accompany the shipment.

4.5.1.2 Storage and coding of DNA samples

The processes adopted for the coding and storage of samples for genetic analysis are important to maintain volunteer confidentiality.

For all samples irrespective of the type of coding used the DNA will be extracted from the blood sample. The DNA sample will be assigned a unique number replacing the information on the sample tube. Thereafter, the DNA sample will be identifiable by the unique DNA number only. The DNA number will be used to identify the sample and corresponding data at the AstraZeneca genetics laboratories, or at the designated contract laboratory. No personal details identifying the individual will be available to any AstraZeneca employee working with the DNA.

The blood samples and data for genetic analysis in this study will be coded. Each blood sample will be labelled with the study number and volunteer number (enrolment/randomisation code). Only the Investigator will be able to link the blood sample to the individual volunteer. The sample and data will not be labelled with a personal identifier. The link between the volunteer enrolment/randomisation code and the DNA number will be maintained.

This link file and any corresponding genetic data will be stored in a secure environment, with restricted access within the [REDACTED] at AstraZeneca, [REDACTED]. The link will be used to identify the relevant DNA samples for analysis, facilitate correlation of genotypic results with clinical data, allow regulatory audit and to trace samples for destruction in the case of withdrawal of consent.

All DNA samples will be stored under secure conditions with restricted access at AstraZeneca and the contracted laboratory. The blood, DNA samples or data derived from the samples may be made available to groups or organisations working with AstraZeneca on this study or as part of the development drug project. However, the samples and any results will remain the

property of AstraZeneca at all times. AstraZeneca will not give blood, DNA samples or data derived from the samples to any other parties, except as required by law.

Samples will be stored for a maximum of 15 years, from the date of completion of the study, after which they will be destroyed.

4.5.1.3 Summary of genetic assessments and analysis

The purpose of the genetic research is to generate data for use in future retrospective analyses. Future analyses will explore genetic factors that may influence the disposition, efficacy, safety and tolerability of AZD9668. The results of the genetic research will not form part of the CSR for this study. The results may be pooled with genetic data from other studies on AZD9668 to generate hypotheses to be tested in future studies.

4.5.1.4 Derivation or calculation of genetic parameters

The number of volunteers who will agree to participate in the genetic research is unknown. It is therefore not possible to establish whether sufficient data will be collected to allow a formal statistical evaluation or whether only descriptive statistics will be generated. A statistical analysis plan will be prepared where appropriate.

4.6 Volume of blood sampling

The total volume of blood that will be drawn from each volunteer in this study is shown in Table 6.

Table 6 Maximum volume of blood to be drawn from each volunteer

Assessment		Sample volume (mL)	n of samples	Total volume (mL)
PD analysis: zymosan stimulated NE activity		4.5	11	49.5
PK analysis		4.0	65	260.0
Pharmacogenetics ^a		10.0	1	10.0
Safety:	Clinical chemistry	8.5	5	42.5
	FSH (Visit 1b)	8.5	1	8.5
	Haematology	3.0	5	15.0
Virology:	Hepatitis B and C and HIV	8.5	1	8.5
Cannula discard (approx.)		1	65	65.0
Total				459.0

^a If consent has been obtained

4.7 Adverse Events

The methods for collecting AEs are described below.

4.7.1 Adverse Events

4.7.1.1 Definitions

The definitions of adverse events (AEs), serious adverse events (SAEs) and other significant adverse events (OAEs) are given below. It is of the utmost importance that all staff involved in the study are familiar with the content of this section. The Principal Investigator is responsible for ensuring this.

Adverse event

An adverse event is the development of an undesirable medical condition or the deterioration of a pre-existing medical condition following or during exposure to a pharmaceutical product, whether or not considered causally related to the product. An undesirable medical condition can be symptoms (eg, nausea, chest pain), signs (eg, tachycardia, enlarged liver) or the abnormal results of an investigation (eg, laboratory findings, electrocardiogram). In clinical studies, an AE can include an undesirable medical condition occurring at any time, including run-in or washout periods, even if no study treatment has been administered.

Serious adverse event

A serious adverse event is an AE occurring during any study phase (ie, run-in, treatment, washout, follow-up), and at any dose of the investigational product, comparator or placebo, that fulfils one or more of the following criteria:

- Results in death.
- Is immediately life-threatening.
- Requires in-patient hospitalisation or prolongation of existing hospitalisation.
- Results in persistent or significant disability or incapacity.
- Is a congenital abnormality or birth defect.
- Is an important medical event that may jeopardise the volunteer or may require medical intervention to prevent one of the outcomes listed above.

The causality of SAEs (ie, their relationship to study treatment) will be assessed by the Investigator, who in completing the relevant case report form must answer “yes” or “no” to the question “Do you consider that there is a reasonable possibility that the event may have been caused by any of the following – study medication – other medication?” For further guidance on the definition of a SAE and a guide to the interpretation of the causality question, see Appendix B to the Clinical Pharmacology Study Protocol.

Note that SAEs that could be associated with any study procedure should also be reported. For such events the causal relationship is implied as “yes”.

Other Significant Adverse Events (OAE)

Other significant adverse events will be identified by the Principal Investigator in consultation with the appropriate Drug Safety Physician during the evaluation of safety data for the CSR. Significant adverse events of particular clinical importance, other than SAEs and those AEs leading to discontinuation of the volunteer from study treatment, will be classified as OAEs. Examples of these are marked haematological and other laboratory abnormalities, and certain events that lead to intervention (other than those already classified as serious), dose reduction or significant additional treatment. For each OAE, a narrative may be written and included in the CSR.

4.7.1.2 Recording of adverse events

Adverse events will be recorded in the CRF from Visit 1b until Visit 5. Any AEs remaining unresolved at Visit 5 should be recorded as “ongoing” in the CRF. Where appropriate, these should be followed as long as medically indicated but without further recording in the CRF.

The following variables will be recorded for each AE: AE description, start and stop date, intensity, action taken, outcome, Investigator’s causality rating (yes or no), and whether the AE meets criteria for a SAE or not.

The following levels of intensity will be recorded:

- mild (awareness of sign or symptom, but easily tolerated).
- moderate (discomfort sufficient to cause interference with normal activities).
- severe (incapacitating, with inability to perform normal activities).

It is important to distinguish between serious and severe AEs. Severity is a measure of intensity whereas seriousness is defined by the criteria in Section 4.7.1.1. An AE of severe intensity need not necessarily be considered serious. For example, nausea that persists for several hours may be considered severe nausea, but not a SAE. On the other hand, a stroke that results in only a limited degree of disability may be considered a mild stroke but would be a SAE.

Adverse events will be collected on an ongoing basis. All AEs spontaneously reported by the volunteer or reported in response to open questions from the study personnel: “Have you had any health problems since the previous visit?” or “Have you had any health problems since you were last asked” or revealed by observation will be collected and recorded in the CRF. The first AE questioning will occur at Visit 1b.

Signs and symptoms present at Visit 1b will be recorded as ‘ongoing pre-dose’. When the severity or seriousness of any pre-dose signs or symptoms changes this will be recorded as a new AE.

Adverse events and any abnormalities in laboratory tests, vital signs or physical examination of clinical relevance will be followed up until resolution. Volunteers who drop out during the study for reasons other than discontinuation of study drug will be followed up for the planned duration of the study. Abnormalities in laboratory tests and vital signs will be recorded and reported in the laboratory reports and CRFs respectively. Abnormalities in these variables will be identified, analysed and reported in the CSR. Laboratory results that constitute a SAE or lead to discontinuation of the study drug will be recorded and reported as an AE. In addition, any abnormality in laboratory tests, which meet the stopping criteria as described in Section 3.1.1, will be recorded as an AE.

Should an overdose (accidental or deliberate) occur, it must be reported in accordance with the procedures described in Section 8.3, ‘Procedures in case of overdose’, regardless of whether the overdose was associated with any symptom or not. All symptoms associated with the overdose should be reported as AEs.

Should a pregnancy occur, it must be reported in accordance with the procedures described in Section 8.4, ‘Procedures in case of pregnancy’. Pregnancy in itself is not regarded as an AE unless there is a suspicion that an investigational product may have interfered with the effectiveness of a contraceptive medication.

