The proposed single dose levels will be 30 mg, 60 mg, 120 mg and 150 mg, although they may change with emerging data from this study. The top dose will be no higher than 150 mg as this is the maximum dose that was administered to healthy volunteers in the AstraZeneca Global SAD/MAD Study (AstraZeneca Protocol Number: D0520C00001 “A Phase I, Randomised, Double Blind, Placebo Controlled, 2-part Study to Assess the Safety, Tolerability and Pharmacokinetics of Single and Multiple Oral Doses of AZD9668 in Healthy Volunteers” Date: [REDACTED]) and was found to be safe. In addition, modelled PK data from the current study will ensure that the predicted geometric mean C_{max} and $AUC_{(0-24)}$ at the top dose will not exceed 2.5 μM or 18 $\mu\text{M}\cdot\text{h}$, respectively. The multiple doses for both cohorts 1 and 2 will be selected following a safety review meetings using emerging data from the current study and the AstraZeneca Global SAD/MAD Study The maximum multiple dose will be capped at a total daily dose of 140 mg. In addition, the emerging PK data from the current study will be modelled to ensure that for the highest dose given, the predicted geometric mean exposures (both $AUC_{(0-24),ss}$ and $C_{max,ss}$) will not exceed 2.5 μM or 18 $\mu\text{M}\cdot\text{h}$, respectively.

Duration of treatment

For each cohort of volunteers, the study will last a minimum of four weeks.

Variables

- Pharmacokinetic

Plasma concentration of AZD9668 is a primary outcome variable and concentration of AZD9668 in urine is a secondary outcome variable.

From these data, the following PK parameters will be derived:

Single dose - Day 1 and 7: C_{max} ; t_{max} ; $AUC_{(0-t)}$; AUC ; $AUC_{(0-12)}$; $AUC_{(0-24)}$; $t_{1/2}$; V_z/F ; CL/F ; CL_R ; A_e ; F_e

Multiple dose - Day 13: C_{max} ; t_{max} ; $AUC_{(0-12)}$; C_{12} ; A_e ; F_e . The A_e and F_e will be estimated using data from 0-12 hours

Day 19: $C_{min,ss}$; $C_{max,ss}$; $t_{max,ss}$; $AUC_{(0-t),ss}$; $AUC_{(0-12),ss}$; $AUC_{(0-24),ss}$; $AUC_{,ss}$; $V_z/F_{,ss}$; $CL/F_{,ss}$; $t_{1/2,ss}$; CL_R ; $A_{e,ss}$; $F_{e,ss}$; R_{ac} ; $C_{12,ss}$

- Pharmacodynamic

The PD outcome variables for AZD9668 are as follows:

Single and multiple dosing – Inhibition of NE activity following zymosan stimulation *ex vivo*.

- Safety

The safety outcome variables for AZD9668 are primary variable, and are as follows:

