6.2 Safety evaluation

6.2.1 Calculation or derivation of safety variables

Adverse events will be analysed by means of descriptive statistics and qualitative analysis, AEs will be listed for each volunteer and summarised by System Organ Class and Preferred Term assigned to event by using MedDRA (Version 10 or higher).

Concomitant medications will be classified according to the AZDD Drug Dictionary, the ATC system and the CPMP route of administration dictionary. All concomitant medications reported at entry and recorded during the study will be listed.

Abnormalities in laboratory safety data, vital signs, ECG or physical examination will only be reported as AEs if they are accompanied by clinical symptoms, constitute SAEs or lead to discontinuation of treatment with the investigational product. For the laboratory safety data, vital signs, and ECG data change from pre dose Visit 2 will be calculated.

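### Section 4.7.1.2 records any change in a pre-dose symptom as a new AE, whereas section 4.7.1.1 counts only deterioration, so an improvement could be logged as an event

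*Protocol*

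**What the plan says.** Section 4.7.1.1 of the protocol defines an adverse event as "the development of an undesirable medical condition or the deterioration of a pre-existing medical condition", arising after or during exposure to a product, whatever its cause.

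Section 4.7.1.2 then sets the recording rules. "Adverse events will be recorded in the CRF from Visit 1b until Visit 5". For the baseline, "Signs and symptoms present at Visit 1b will be recorded as" ongoing pre-dose. The next sentence is the one at issue: "When the severity or seriousness of any pre-dose signs or symptoms changes this will be recorded as a new AE". Each AE carries its own set of fields, including "AE description, start and stop date, intensity, action taken, outcome", followed by the Investigator's yes/no causality rating and whether the event is serious. Intensity has three levels: mild, moderate and severe.

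On use of the data, the synopsis (Variables) gives safety primary status: "The safety outcome variables for AZD9668 are primary variable". Section 6.2.1 says that "AEs will be listed for each volunteer and summarised by System Organ Class and Preferred Term". Section 6.4.4 summarises data by dose administered, with percentages taken over all volunteers in the treatment group.

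**The concern.** The definition has a direction and the recording rule does not. A symptom that was moderate at Visit 1b and is mild after dosing has neither newly developed nor deteriorated, so it is not an AE under section 4.7.1.1. Under section 4.7.1.2 it must be entered as one. The same holds for seriousness: a step down from serious is also a change.

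Such a record would have a start date after dosing and would prompt a causality judgement about study drug. It would then sit in the listings and summaries of a primary variable, in groups small enough for one volunteer to move a percentage visibly. There is also a consistency problem at the point of collection, because two members of staff could follow two current sentences of the protocol and record the same course differently.

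**Working it through.** The plan gives no figure to reproduce, and the study has no hypothesis test or formal powering. The check is therefore a comparison of the two rules, followed by the weight of one record.

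**Step 1: the two rules side by side.** Inputs are the definition (section 4.7.1.1), and the recording rule and three-level intensity scale (both section 4.7.1.2).

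| Intensity at Visit 1b | Possible change in intensity | New AE under the 4.7.1.2 rule | AE under the 4.7.1.1 definition |
|---|---|---|---|
| Mild | to moderate or severe | yes | yes |
| Moderate | to severe | yes | yes |
| Moderate | to mild | yes | no |
| Severe | to moderate or mild | yes | no |

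The rules agree on every worsening and disagree on every improvement. A disagreement needs a baseline of moderate or severe. A mild symptom can only move up the scale, and its disappearance is captured by the stop date.

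**Step 2: which improvements get a post-dose date.** Recording runs from Visit 1b, up to 21 days before Visit 2. An improvement between Visit 1b and the first dose would also create a record under the literal rule, but one dated before dosing. Only improvements after the first dose give a post-dose start date.

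**Step 3: size of one such record.** Sections 3.1 and 3.4.3 allocate each cohort of eight in a 6:2 ratio of active to placebo within each ethnic group, and parallel Japanese and Caucasian cohorts receive the same dose.

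- Active volunteers per dose level: 6 in one ethnic group; 6 + 6 = 12 with both groups together.
- Added incidence on active: 1/6 = 16.7 percentage points in one ethnic group; 1/12 = 8.3 points with both together.
- Added incidence on placebo: 1/2 = 50 points in one ethnic group of a cohort; 1/4 = 25 points with both ethnic groups of that cohort together.
- Under a rule limited to worsening: 0 in every case.

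These increments apply only if the volunteer has no other AE in the same category. Otherwise the event count rises by one and the volunteer incidence does not change. The active figures also assume that a dose level is not repeated in another cohort.

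**Step 4: how often.** The protocol gives no number of volunteers with pre-dose symptoms, so no expected total can be calculated. Inclusion criterion 6 requires normal examination, laboratory values and vital signs unless an abnormality is judged clinically irrelevant. Exclusion criterion 2 removes volunteers with symptoms of clinically significant illness in the two weeks before Visit 2. Both point to few moderate or severe baselines.

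**The case against.** The strongest reply is that the definition governs. The sentence in section 4.7.1.2 creates an AE, AE is defined one subsection earlier, and section 4.7.1.1 stresses that all staff must know that definition and makes the Principal Investigator responsible for this. Read together, only worsening would qualify. This is a fair reading, and it is why miscounting should be described as possible and not as certain. It does not remove the contradiction: the recording sentence is mandatory and is the more specific of the two.

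A second reply is that the statistical analysis plan, which is not shown, could filter such records, since the pre-dose entry and the intensity of the new record are both collected. That could repair the final tables, provided each new record can be traced to its pre-dose entry; the protocol states no such link. It would not reach the safety data that the Investigator and the Safety Review Committee see between dose levels.

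Third, nothing is tested. The escalation criteria in section 3.1.1 rest on laboratory, ECG and exposure limits and on the Investigator's judgement, not on AE counts. The rule also applies alike to active and placebo under blinding, so it adds noise and does not favour either arm. All of this stands and limits the importance of the point.

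Two stronger readings are tempting but not supported:

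- A reader might infer that a symptom going from mild to moderate and back to mild yields two new AEs. The rule concerns pre-dose symptoms. Once the moderate episode is its own AE, the return to mild can simply close it, and no sentence makes a change within an on-study AE a further AE. Even if it were entered twice, volunteer incidence would not move.
- A reader might infer that about half of the AEs created by this rule are false, on the idea that symptoms vary symmetrically. The scale rules out symmetry for mild baselines, which are the likely ones in this population, and the protocol has no data on the rest.

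**Conclusion.** The contradiction between sections 4.7.1.1 and 4.7.1.2 is real and rests on the text alone. Followed literally, the recording rule turns the improvement of a moderate or severe pre-dose symptom into a new AE in a primary safety variable; followed through the definition, it does not.

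The consequence is probably small. The increments of 8.3 and 16.7 points describe a single improvement on active drug, after dosing, in a volunteer with no other AE in that category. They are not a general effect on the AE tables. The label *on-treatment* is also an inference from the start date and the summaries by dose, because the protocol does not define treatment-emergent events. The documents do not show that the primary safety data will be distorted. They show a stated rule that gives a wrong record in a rare case and may be applied inconsistently. Low severity, worth correcting because the correction is so cheap.

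**What to change.** In section 4.7.1.2, limit the rule to worsening, for example:

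> *A pre-dose sign or symptom is entered as a new AE only if its severity increases above the pre-dose level or it becomes serious. Improvement is noted in the existing entry and is not a new AE.*

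The CRF completion guide should carry the same wording. The cost is one sentence in each document, with no extra data, visits or volunteers. Every deterioration would still be recorded, so no safety information is lost.
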